5.3.9.3. Cardiac Safety

Cardiac safety data from this study will be provided to France regulatory authorities on a periodic basis (every 6 months from first patient visit) and will be assessed through echocardiography, ECG, chest CT scan, ECG chemistry and cardiac related adverse events.

Echocardiography, ECG and ECG chemistry will be assessed at screening for enrollment, predose at every other cycle starting from Cycle 2 (C2, C4, C6), at Visit 801 and follow-up. If the patient has clinically significant cardiac findings at discontinuation (Visit 801), echocardiography, ECG and ECG chemistry will be repeated every 2 months for 6 months (Visits 803, 805, and 807).

Chest CT scan will be assessed at screening for enrollment, every 6 months from first assessment and at discontinuation (Visit 801). Alternatively, chest and/or abdomen MRI are performed. If there were no clinically significant findings at the last assessment conducted within the last 30 days and the patient has started another treatment, Visit 801 CT scan or chest MRI with contrast will not be performed.

If there are no clinically significant cardiac findings at discontinuation (Visit 801), 1 more echocardiography, ECG, and ECG chemistry will be performed after 2 months (Visit 803). If a patient receives another treatment, Visit 803 cardiac assessments will not be performed.

A central reading will be performed for the data used in the final study report.

ECG data will be listed as qualitative and quantitative data separately. Qualitative ECG data includes information on rhythm, conduction, normality, morphology, ST segment, T wave and U wave. Quantitative ECG data listing would include PR, QRS, QTcb, and QT intervals.

Occurrence of cardiac related AE data such as myocardial ischemia, myocardial injury and myocardial infarction will also be included in this listing.

Plots of change from baseline in QTcF versus PK concentrations will be provided. Summary statistics of for QTcB and QTcF will be provided. Number of patients with maximum change from baseline in QTcF > 30 msec and > 60 msec and raw QTcF > 450 msec, > 470 msec and > 500 msec will be provided.

A listing of all ECG chemistry for Lipase, Thyroid Stimulating Hormone (TSH), Tri-iodothyronine (T3) and Thyroxine (T4) will be provided. Cardiac related adverse events (SOC='cardiac disorders') including their CTCAE grade will be listed.

Echocardiography measurement data will be listed separately. One listing will include variables such as LV internal dimension, LA volume, LA dimension, LV ejection fraction and LV mass. The other listing will include PA systolic pressure, pulmonary flow velocity acceleration time, mitral deceleration time, mitral E/A ratio, E/Em, RA dilation and RV dilation. Plot of LV ejection fraction over time will be provided. Echocardiography assessments with regurgitation,

wall motion, pericardial effusion data will be listed, Patient listings of changes in echocardiographic measurements from baseline to post-dose visits will also be provided separately for the variables above. In addition, overall ECG assessments recorded from GLS and on CRF (including clinical significance) will be listed. Summary on the frequency of maximum change from baseline for RA dilation, RV dilation, left ventricular wall motion, pericardial effusion and valvular regurgitations will be provided.

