5.1.7. Rationale for Amendment (b)

The protocol is amended for the following reasons:

As part of the continuous monitoring of safety, PK, and laboratory markers in patients with HCC, the sponsor noted that patients are staying on study beyond 4 months. Furthermore, the 300 mg/day dose appears to have no evidence of increased toxicity. There appears to be no difference in the number of patients at the 160-mg/day and the 300-mg/day dose who stayed beyond 4 months. In addition, in all other ongoing trials with LY2157299, the dose of 300 mg/day was selected for future clinical development.

Preliminary PK data from the first interim analysis (n=20 patients) suggest that patients administered 300 mg/day have higher exposures than previously observed for the same dose level (Study JBAH) during the treatment period. LY2157299 appears to be fully eliminated after the 14-days off period of a cycle (additional PK sampling is added to study the clearance of LY2157299). The lowest exposure level (ie, most conservative) in the most sensitive nonclinical species administered LY2157299 in a clinically relevant dosing schedule (2 weeks on/2 weeks off) in which cardiac effects were observed was 24 $\mu\text{g}\cdot\text{hr}/\text{mL}$ (Table JBAK.2). The findings at this dose level (150 mg/kg) consisted of a single male rat (n=10/group) with minimal inflammation in the aortic valve and ascending aorta. Administration of 300 mg/day to patients with HCC may result in higher than anticipated exposures; however, due to the clinical safety profile observed thus far and the benefit:risk in this patient population, this approach is considered acceptable.

Because of these reasons and the lack of substantial evidence that the 160-mg/day dose is superior to the 300-mg/day dose, the dose of 300 mg/day is selected for the continuation of this trial.

For Part B, it was decided to evaluate the effects of LY2157299 in patients with AFP <1.5x upper limit of normal (ULN) to have an overall assessment of LY2157299 efficacy in all HCC patients. At the time of the decision to focus on the 300-mg/day dose, 74 patients were randomized.

The study design will be modified as follows:

- Part A: Evaluation of LY2157299 in Child-Pugh A or B7 patients with AFP $\geq 1.5x$ ULN. After stopping the 160-mg/day dose arm, all newly enrolled patients will be treated at the 300-mg/day dose.
- Part B: Evaluation of LY2157299 in Child-Pugh A or B7 patients with AFP <1.5x ULN

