10.2.3. Electrocardiography

For each subject, 12-lead digital ECGs will be obtained as single ECGs according to the Study Schedule ([Attachment 1](#)). Patients must be supine for approximately 5 to 10 minutes before ECG collection and remain supine during ECG collection. ECGs may be obtained at additional times, when deemed clinically necessary. Collection of more ECGs than expected at a particular time point is allowed when needed to ensure high-quality records.

ECGs will be interpreted by a qualified physician (the investigator or qualified designee) at the site as soon after the time of ECG collection as possible, and ideally while the patient is still present, to determine whether the patient meets entry criteria and for immediate patient management, should any clinically relevant findings be identified.

If a clinically significant quantitative or qualitative change from baseline is identified after enrollment, the investigator will assess the patient for symptoms (for example, palpitations, near syncope, syncope) and to determine if the patient can continue in the study. The investigator or qualified designee is responsible for determining if any change in patient management is needed and must document his/her review of the ECG printed at the time of evaluation.

All digital ECGs will be electronically transmitted to a central ECG laboratory designated by Lilly. A cardiologist at the central ECG laboratory will then conduct a full overread on the ECG (including all intervals); a report based on data from this analysis will be issued to the investigative site. All data from the overreads will be placed in the Lilly database for analytical and study-report purposes.

It is recognized that ECG interpretations by the investigator (or qualified designee) and by the cardiologist at the central ECG laboratory may be different. When there are differences in ECG interpretation between the investigator (or qualified designee) and the cardiologist at the central ECG laboratory, the investigator (or qualified designee) interpretation will be used for study entry and immediate subject management. Interpretations from the cardiologist at the central ECG laboratory will be used for data analysis and report-writing purposes.

The investigator (or qualified designee) must document his/her review of the ECG printed at the time of evaluation, the final overread ECG report issued by the central ECG laboratory, and any alert reports.

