Attachment 1. Protocol JBAK Study Schedule

Parts A and B

Cycle/Visit ^j	Prestudy			Cycle 1					Cycle 2		Cycle 3, n ^l		Extension Period	Visit 801	Follow-up ^f	Comments
	≤28	≤14	≤7	1 ⁱ	8 ⁱ	14 ⁱ	15	22	1 ⁱ	14 ^{i,k}	1 ⁱ	14 ^{i,k}				
Procedures																
Informed Consent	X															Informed consent must be signed prior to performing any study procedures.
Medical History		X														
Child-Pugh, Barcelona Clinic Liver Cancer (BCLC), and CLIP staging			X ^h													
Pregnancy Test			X													
Physical Exam		X		X		X			X	X	X		X	X		Starting in Cycle 3, to be performed once per cycle. Perform predose on Day 1 of each cycle in extension period.
Vital Signs (heart rate, blood pressure)		X		X		X			X	X	X		X	X		Starting in Cycle 3, to be performed once per cycle. Perform predose on Day 1 of each cycle in extension period.
CTCAE Grading		X		X		X			X	X	X		X	X	X ^a	Starting in Cycle 3, to be performed once per cycle. Perform predose on Day 1 of each cycle in extension period.
Concomitant Medications		X		X					X		X		X	X	X	Perform predose on Day 1 of each cycle in extension period.
Performance Status		X		X		X			X	X	X		X	X		Starting in Cycle 3, to be performed once per cycle. Perform predose on Day 1 of each cycle in extension period.

Cycle/Visitj	Prestudy			Cycle 1					Cycle 2		Cycle 3, n ^l		Extension Period	Visit 801	Follow-up ^f	Comments
	≤28	≤14	≤7	1 ⁱ	8 ⁱ	14 ⁱ	15	22	1 ⁱ	14 ^{i,k}	1 ⁱ	14 ^{i,k}				
Tumor Assessment, Physical (Palpable or Visible)		X		X					X		X			X		Optional during the extension period (including extension period V801)
Imaging Procedures																
Echocardiography with Doppler ^g	X								X		X		X	X ^b	X ^b	Cycle 2, 3, 4, and every other cycle (C6, C8,...etc). Perform predose on Day 1 of each cycle in extension period
Chest CT Scan or Chest MRI		X											X	X ^c		CT scan or MRI every 6 months
Tumor Assessment, Radiological		X								X	X			X ^d	X ^d	Tumor assessment every 6 weeks starting Cycle 2, Day 14. May be performed 3 days around the scheduled date. Optional during the extension period (including extension period V801)
ECG		X							X		X		X	X ^b	X ^b	Cycle 2, 3, 4, and every other cycle (C6, C8,...etc). Perform predose on Day 1 of each cycle in extension period

Cycle/Visit ^j	Prestudy			Cycle 1					Cycle 2		Cycle 3, n ^l		Extension Period	Visit 801	Follow-up ^f	Comments
	≤28	≤14	≤7	1 ⁱ	8 ⁱ	14 ⁱ	15	22	1 ⁱ	14 ⁱ , k	1 ⁱ	14 ⁱ , k				
Laboratory /Diagnostic Tests																

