ECG chemistry		X							X		X		X	X ^b	X ^b	Cycle 2, 3, 4, and every other cycle (C6, C8,...etc). Perform predose on Day 1 of each cycle in extension period. Can be done at local labs during the extension period
Special chemistry			X		X	X		X	X	X	X	X	X	X		Perform predose on Day 1 of each cycle in extension period. Can be done at local labs during the extension period
Hematology			X		X	X		X	X	X	X	X	X	X		Perform predose on Day 1 of each cycle in extension period. Can be done at local labs during the extension period
Serum chemistry			X		X	X		X	X	X	X	X	X	X		Perform predose on Day 1 of each cycle in extension period. Can be done at local labs during the extension period
Urinalysis		X							X		X			X		Optional during the extension period (including extension period V801)
Urine C-terminal telopeptides of Type 1 collagen		X							X		X					Optional during the extension period

Cycle/Visit ^j	Prestudy			Cycle 1					Cycle 2		Cycle 3, n ^l		Extension Period	Visit 801	Follow-up ^f	Comments
	≤28	≤14	≤7	1 ⁱ	8 ⁱ	14 ⁱ	15	22	1 ⁱ	14 ⁱ , k	1 ⁱ	14 ⁱ , k				
PK sampling ^e				X		X	X	X	X		X					Timed with ECG
Serum markers (AFP, AFP L3, E-cadherin, PIVKA II)		X		X		X			X	X	X	X	AFP only	X		Perform predose on Day 1 of each cycle in extension period. Can be done at local labs during the extension period
Immuno-phenotype				X					X		X			X		Optional during the extension period (including extension period V801)
TGF-β+PF4		X		X		X			X	X	X	X		X		Optional during the extension period (including extension period V801)
MAP panel		X				X				X		X		X		Optional during the extension period (including extension period V801)
Fibrotest		X				X				X		X				
aPTT/PT/ INR		X		X					X		X		X			Perform predose on Day 1 of each cycle in extension period. Can be done at local labs during the extension period
Patient-Reported Outcomes																
FACT-Hep		X							X		X			X		Optional during the extension period (including extension period V801)

Cycle/Visit ^j	Prestudy			Cycle 1					Cycle 2		Cycle 3, n ^l		Extension Period	Visit 801	Follow-up ^f	Comments
	≤28	≤14	≤7	1 ⁱ	8 ⁱ	14 ⁱ	15	22	1 ⁱ	14 ^{i,k}	1 ⁱ	14 ^{i,k}				
Relative Day Within a Cycle																
Translational Research																
Whole blood for PGx		X														
Obtained diagnostic tumor tissue, when available		X														
Optional tumor biopsy	X								X							+/- 3 days after end of treatment with LY2157299

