Special chemistry			X		X	X		X	X	X	X	X	X	X		Perform predose on Day 1 of each cycle in extension period. Can be done at local labs during the extension period
Hematology			X		X	X		X	X	X	X	X	X	X		Perform predose on Day 1 of each cycle in extension period. Can be done at local labs during the extension period
Serum chemistry			X		X	X		X	X	X	X	X	X	X		Perform predose on Day 1 of each cycle in extension period. Can be done at local labs during the extension period
Urinalysis		X							X		X			X		Optional during the extension period (including extension period V801)
Urine C-terminal telopeptides of Type 1 collagen		X							X		X					Optional during the extension period

Cycle/Visit ^j	Prestudy			Cycle 1					Cycle 2		Cycle 3, n ^l		Extension Period	Visit 801	Follow-up ^f	Comments
	≤28	≤14	≤7	1 ⁱ	8 ⁱ	14 ⁱ	21	22	1 ⁱ	14 ⁱ , k	1 ⁱ	14 ⁱ , k				
PK sampling ^e				X			X	X	X		X					Timed with ECG. See Attachment 4 for specific timepoints.
Serum markers (AFP, AFP L3, E-cadherin, PIVKA II)		X		X			X		X		X		AFP only	X		Perform predose on Day 1 of each cycle in extension period. Can be done at local labs during the extension period
Immuno-phenotype				X					X		X			X		Optional during the extension period (including extension period V801)
TGF-β+PF4		X		X			X		X		X			X		Optional during the extension period (including extension period V801)
MAP panel				X			X		X		X			X		Optional during the extension period (including extension period V801)
Fibrotest		X					X		X		X					
aPTT/PT/ INR		X		X					X		X		X			Perform predose on Day 1 of each cycle in extension period. Can be done at local labs during the extension period
Patient-Reported Outcomes																
FACT-Hep		X							X		X			X		Optional during the extension period (including extension period V801)

Cycle/Visit ^j	Prestudy			Cycle 1					Cycle 2		Cycle 3, n ^l		Extension Period	Visit 801	Follow-up ^f	Comments
	≤28	≤14	≤7	1 ⁱ	8 ⁱ	14 ⁱ	21	22	1 ⁱ	14 ^{i,k}	1 ⁱ	14 ^{i,k}				
Translational Research																
Whole blood for PGx		X														
Obtained diagnostic tumor tissue, when available		X														
Optional tumor biopsy	X								X							+/- 3 days after end of treatment with LY2157299

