Abbreviations: AFP = alpha-fetoprotein; aPTT = activated partial prothrombin time; C = cycle; CLIP = Cancer of the Liver Italian Program; CT = computerized tomography; CTCAE = Common Terminology Criteria for Adverse Events; D = Day; ECG = electrocardiogram; FACT = Functional Assessment of Cancer Therapy; INR = international normalized ratio; MAP = multi-analyte panel; MRI = magnetic resonance imaging; PGx = pharmacogenomics; PIVKA II = prothrombin induced by vitamin K absence; PK = pharmacokinetic; PT = prothrombin time; TGF-β = transforming growth factor beta.

- a If drug-related toxicity is present 30 days after last cycle of study drug, patients must be followed up approximately every 30 days until toxicity resolution, stabilization, another therapy is initiated, or death.
- b If the patient has clinically significant cardiac findings at discontinuation (V801), echocardiography with Doppler, ECG, and ECG chemistry will be repeated every 2 months for 6 months (V803, V804, and V805). If there are no cardiac findings at discontinuation (V801), 1 more echocardiography with Doppler, ECG, and ECG chemistry will be performed after 2 months (V802) unless a patient is receiving another treatment (see Section 10.2.4).
- c If there were no clinically significant findings at the last assessment conducted within the 30 days following discontinuation and the patient has started another treatment, Visit 801 CT scan or chest MRI with contrast will not be performed.
- d Repeat radiological scans at study discontinuation may be omitted if a patient has objective disease progression or if imaging has been performed in the previous 3 to 6 weeks.
- e For details, see Attachment 4. PK sampling will be performed on Cycle 1, with a predose sample on Day 1 of Cycle 2 and all subsequent cycles.
- f Follow-up consists of Visit 802 and all subsequent visits (60 days ±7 days). All patients will be followed for OS until study completion.
- g Echocardiogram with Doppler can be performed up to 3 days prior to Day 1.
- h Child-Pugh, BCLC, and CLIP assessment procedures can be found in Attachment 5, Attachment 6, and Attachment 7, respectively.
- i To be performed predose LY2157299.
- j A delay at the start of a cycle (Day 1) of no more than 3 days, because of holidays, weekends, inclement weather, or other justifiable events, will be permitted and not counted as a protocol violation.

- k In extenuating circumstances, the 'on study drug' window is allowable from Day 10 to Day 14.

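### The ECG rows and the SAP mark no on-treatment ECG while LY2157299 is on board, which conflicts with the PK-row comment and with the planned QTcF-versus-concentration plot

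*SAP*

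**What the plan says.** SAP section 5.3.9.3 (Cardiac Safety) plans the following: "Plots of change from baseline in QTcF versus PK concentrations will be provided". It adds summary statistics for QTcB and QTcF, and counts of patients with a QTcF change above 30 and 60 msec or a value above 450, 470 and 500 msec. The same section places the ECG "predose at every other cycle starting from Cycle 2 (C2, C4, C6), at Visit 801 and follow-up".

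Protocol section 10.2.3 lets the Study Schedule govern: "12-lead digital ECGs will be obtained as single ECGs according to the Study Schedule". In Attachment 1 the ECG row has the same pattern in every part: prestudy, Day 1 of Cycle 2 and later cycles, the extension period, Visit 801 and follow-up. The Parts A/B comment reads "Cycle 2, 3, 4, and every other cycle (C6, C8,...etc). Perform predose on Day 1 of each cycle in extension period". The Day 1 columns carry footnote i, which for Parts A/B and E reads "To be performed predose LY2157299"; in Parts C and D it adds the partner drug. No ECG is marked in Cycle 1 or on any last dosing day.

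The PK rows point the other way in two places. In Parts A/B the comment is "Timed with ECG", on a row marked on Cycle 1 Days 1, 14, 15 and 22 as well as on later Day 1 visits. In Part E it is "Timed with ECG. See Attachment 4 for specific timepoints", on a row marked on Cycle 1 Days 1, 21 and 22 and later Day 1 visits. Parts C and D have no such comment.

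On washout, protocol section 5.1.7 states: "LY2157299 appears to be fully eliminated after the 14-days off period of a cycle".

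**The concern.** A QTcF-concentration plot needs ECGs taken across a range of concentrations. If sites follow the ECG rows, each on-treatment ECG is taken at the end of the off period, and the only PK sample at the same nominal time is a predose one. The concentration axis then collapses to about zero. The outlier counts would describe washed-out patients. In Part C, where sorafenib runs through Days 1 to 28, they would describe patients on sorafenib but without LY2157299.

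A clean result could then be read as evidence that the drug has no acute effect on repolarisation, which these ECGs could not show. The output has readers beyond the study report: SAP 5.3.9.3 sends cardiac safety data to a national regulator every 6 months.

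**Working it through.** **Step 1: where ECGs and drug-carrying samples fall** (Attachments 1 and 4). On-treatment ECGs are at Day 1 predose from Cycle 2 in every part.

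| Part | Post-dose LY2157299 samples | PK sample at the same nominal time as a marked ECG |
|---|---|---|
| A, B, C expansion | C1 D1 (0.5-2 h); C1 D14 (0.5-2 h, 3-5 h) | Predose Day 1 only |
| C lead-in | C1 D1 and D14 (0.5, 2, 3, 6 h); C2 D1 (0.5-2 h); C2 D14 (0.5-2 h, 3-5 h) | Predose Day 1 only |
| D | C1 D1 (1.5-3 h); C1 D14 (0.5, 2, 3, 6 h); C2 D1 (1.5-3 h); C2 D14 (0.5-2 h, 3-5 h) | Predose Day 1 only |
| E | C1 D1 (0.5-2 h); C1 D21 (0.5-2 h, 3-5 h) | Predose Day 1 only |

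In the Part C lead-in and Part D, Cycle 2 Day 1 has both a predose ECG and a post-dose sample. Merging by visit rather than by time would pair a drug-free QTcF with an on-drug concentration and push the plot towards no relationship.

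**Step 2: check the PK inputs.** Protocol section 5.1.3 gives clearance 38.4 L/h and Vss 193 L. Daily AUC = dose/CL: 160/38.4 = 4.17 and 300/38.4 = 7.81 µg·h/mL. Table JBAK.2 gives simulated once-daily values of 4.1 and 7.7, so they agree within 1.6%.

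**Step 3: half-life** (one-compartment approximation; the fitted model has two compartments). k = CL/Vss = 38.4/193 = 0.199 per h, so t½ = ln 2/0.199 = 3.48 h. Predicted twice-daily accumulation is 1/(1 − exp(−12 × 0.199)) = 1.10, against the stated value of about 1. Section 5.1.1 gives 4 to 8 h in animals; I use 8 h as a slow bound and 24 h as an assumed extreme.

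**Step 4: drug-free interval before a Day 1 ECG.** Nominally it is 14 days (A to D) or 7 days (E). Section 7.1 allows cycles of 26 to 31 days with 10 to 14 dosing days in Parts A to D, so the range there is 26 − 14 = 12 to 31 − 10 = 21 days. In Part E the shortest gap is 26 − 21 = 5 days.

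**Step 5: residual fraction** = 0.5^(hours off/t½).

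| t½ | 1 day | 5 days | 7 days | 14 days |
|---|---|---|---|---|
| 3.48 h | 0.84% | 4.3e-11 | 3.0e-15 | 9.3e-30 |
| 8 h | 12.5% | 3.1e-5 | 4.8e-7 | 2.3e-13 |
| 24 h (assumed) | 50% | 3.1% | 0.78% | 0.006% |

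To leave 1% of the last level, t½ would have to be about 25 h at 7 days or 51 h at 14 days (hours × ln 2/ln 100).

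**Step 6: Visit 801.** Section 10 lets it open 1 day after discontinuation, so residual drug of roughly 0.8% to 12.5% is possible if the last dose was the day before. No PK sample is scheduled there, so this ECG cannot enter the plot.

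**The case against.** The best counter-argument is that the PK-row comment in Parts A/B and E already ties ECGs to Cycle 1 dosing-day samples, and that the SAP plot presupposes such pairs. That reading is fair. A reader might infer from the ECG rows that every ECG in the study is drug-free; the documents do not support that. The comment may mean that on-drug ECGs were taken, and Visit 801 can fall soon after the last dose. What stands is a contradiction: the ECG row and the SAP timing text say one thing, the comment another, and a site cannot tell which to follow.

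Importance is also limited. Section 5.1.4 reports no substantive nonclinical QT risk at plasma concentrations of at least 3.3 µg/mL. The measured daily AUC of 4.3 µg·h/mL at 300 mg/day averages 4.3/24 = 0.18 µg/mL. That is an average, not a peak, and section 5.1.7 notes higher exposure in HCC than in the earlier study. The cardiac hazard that drives monitoring is valvular and vascular, followed by echocardiography, chest imaging, cardiac markers and adverse events. A reader might infer that cardiac safety as a whole goes unassessed; it does not. Off-drug ECGs may also serve to detect delayed effects, and unscheduled ECGs are allowed when clinically needed.

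Two further inferences fail. Sorafenib's own QT effect is not hidden in Part C, because dosing is continuous and Day 1 ECGs from Cycle 2 are taken on sorafenib; only an effect of the combination at LY2157299 exposure would be missed. And what will be reported for the 21/7 schedule cannot be read from the supplied SAP, which is aligned with Amendment (c) and covers Parts A to C. Protocol section 12.2.8 promises later versions for Parts D and E.

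**Conclusion.** The point holds as a conflict between documents with a definite consequence. Followed as written, the ECG rows and SAP 5.3.9.3 give on-treatment QTcF values at essentially zero LY2157299: below 1e-6 of the last level at the nominal gaps, and about 3e-5 at worst with the shortest permitted Part E gap and an 8 h half-life. The plot would then be uninformative, and the on-treatment outlier counts would be off-drug counts.

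This rests on the protocol's population parameters, a one-compartment approximation and the 8 h bound. For the 14-day gap the protocol's own washout statement supports it independently. It is conditional on ECGs not having been taken beside the post-dose samples, which the documents leave open. Severity is moderate: QTcF is descriptive and carries no study objective of its own. Schedule changes can reach only Part D (about 18 patients, already enrolling) and Part E (about 23), since enrolment in Parts A to C is complete.

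**What to change.** 1. Reconcile the ECG row, the PK-row comment and SAP 5.3.9.3, so that all three name the same ECG times.
2. In Parts D and E, move one existing Day 1 ECG to the last dosing day of Cycle 1, beside a PK sample already scheduled: Day 14 at the 0.5 h or 2 h sample in Part D, Day 21 in the 0.5-2 h window in Part E.
3. In the SAP, limit the QTcF-concentration plot to ECGs paired in time, not merely by visit, with a post-dose sample. Report outlier counts separately for on-drug and off-drug ECGs. Carry this into the SAP versions for Parts D and E.
4. For Parts A to C, check whether paired ECGs exist. If not, label the QTcF tables as off-LY2157299 values and drop the plot.

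The cost is an edit to the schedule tables through an amendment and a few SAP sentences. Moving an ECG needs no extra visit, ECG or PK sample, but leaves one fewer off-drug ECG taken alongside the echocardiogram and ECG chemistry. If that ECG is wanted for delayed effects, adding one instead of moving it costs a single extra ECG per patient at a visit already attended.
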